### **8.2.5      Pregnancy**

All pregnancies and outcomes of pregnancy should be reported to AstraZeneca except for the study participant whose pregnancy is discovered before receiving any study drug.

#### **8.2.5.1    Maternal Exposure**

If a participant becomes pregnant during the study, benralizumab should be discontinued immediately.

Pregnancy itself is not regarded as an AE unless there is a suspicion that benralizumab may have interfered with the effectiveness of a contraceptive medication. Congenital abnormalities/birth defects and spontaneous miscarriages should be reported and handled as SAEs. Elective termination of pregnancy without complications should not be handled as AEs. The outcome of all pregnancies (spontaneous miscarriage, elective termination, ectopic pregnancy, normal birth or congenital abnormality) should be followed up and documented even if the participant was discontinued from the study.

If any pregnancy occurs in the course of the study, then the investigator or other site personnel informs the appropriate AstraZeneca representatives within **1 day**, ie, immediately but **no later**

The designated AstraZeneca representative works with the investigator to ensure that all relevant information is provided to the AstraZeneca Patient Safety data entry site **within 1 or 5 calendar days** for SAEs (see [Section 8.2.4](#)) and **within 30 days** for all other pregnancies.

The same timelines apply when outcome information is available.

#### **8.2.5.2 Paternal Exposure**

Pregnancy of the participant's partners will not be considered an AE. However, the outcome of all pregnancies (spontaneous miscarriage, elective termination, ectopic pregnancy, normal birth, or congenital abnormality) should be followed up and documented in the Pregnancy Report Form. Consent from the partner must be obtained before the Pregnancy Report Form is completed.

### **8.3 Effectiveness Assessments**

#### **8.3.1 Assessment of Asthma Exacerbations**

For the protocol, an asthma exacerbation will be defined as a worsening of asthma that leads to any of the following:

- Use of systemic corticosteroids (or a temporary increase in a stable OCS background dose) for at least 3 days; a single depot-injectable dose of corticosteroids will be considered equivalent to a 3-day course of systemic corticosteroids.
- An ER/Urgent care visit (defined as evaluation and treatment for <24 hours in an emergency department or urgent care centre) due to asthma that required systemic corticosteroids (as per above).
- An inpatient hospitalisation (defined as admission to an inpatient facility and/or evaluation and treatment in a healthcare facility for ≥24 hours) due to asthma.

Time to first asthma exacerbation will be calculated from baseline (Day 1) to time of first exacerbation. The start of an exacerbation is defined as the start date of systemic corticosteroids, ER or urgent care visits requiring systemic corticosteroids, or hospital admissions due to asthma, whichever occurs earlier. The end date is defined as the last day of systemic corticosteroids or ER/Urgent care/hospital discharge, whichever occurs later.

In order to calculate the number of exacerbations experienced by a patient during the study period, the following rule will be applied. The start of an exacerbation is defined as the start date of systemic corticosteroids or start date of a temporary increase in a stable OCS background dose, or start date of hospital admission, whichever occurs earlier. The end date is defined as the last day of systemic corticosteroids or the last day of a temporary increase in a stable OCS background

Version: 1.0 Dated 09 Mar 2021

dose, or the date of discharge from a hospital, whichever occurs later. Additional systemic corticosteroid treatments, ER/urgent care visits requiring use of systemic corticosteroids, or inpatient hospitalisation due to asthma occurring during an exacerbation should not be regarded as a new exacerbation. In order to be counted for as a new exacerbation it must be preceded by at least 7 days in which neither criterion is fulfilled.

Maximum follow-up time for a participant is approximately 24 weeks; defined as the time from enrolment to the date of EOS visit. For a participant lost to follow-up, this will be defined as the time from enrolment to the time point after which an exacerbation could not be assessed, (ie, the last contact date). Any exacerbations after this time point will not be included in analyses.

Proportion of participants with  $\geq 1$  asthma exacerbation(s) between baseline and end of study will be summarised.

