**Table 1 Schedule of Activities**

Procedure	Screening (Up to 14 Days Before Day 1)	Intervention Period				Follow-up EOS Week 24
		Day 1	Week 4	Week 8	(Last Dose) Week 16	
Visit		1	2	3	4	5
Informed consent	X					
Inclusion and exclusion criteria a	X					
Demography, anthropometry including BMI	X					
Significant medical history	X					
Clinical safety laboratory assessments b	X					X
Serum/urine pregnancy test (WOCBP only) c	X	X	X	X	X	X
Vital signs d	X	X	X	X	X	X
ECG	X		X			X
Targeted physical examination	X	X	X	X	X	X
Blood eosinophil count	X		X		X	X
Prebronchodilator FEV1	X					
Postbronchodilator FEV1 e	X					
Administration of benralizumab		X	X	X	X	
Recording Use of concomitant asthma medication (OCS/ICS/LABA)	X	X	X	X	X	X
Adverse events and Serious adverse events f (reported g and observed)	X	X	X	X	X	X
Assessment of asthma exacerbations	X	X	X	X	X	X

Abbreviations: BMI = body mass index; EOS = end of study; ECG= Electrocardiogram; FEV1 = forced expiratory volume in one second; ICS = inhaled corticosteroid; LABA = long-acting beta-agonist; OCS = oral corticosteroid; UPT = urine pregnancy test; WOCBP = women of childbearing potential (after menarche)

Version: 1.0 Dated 09 Mar 2021

a Recheck clinical status before first dose of benralizumab.

b Clinical safety laboratory assessment will include clinical chemistry, haematology, and urinalysis. Clinical chemistry will include serum alkaline phosphatase, alanine aminotransferase, aspartate aminotransferase, gamma-glutamyl transferase, lactate dehydrogenase, total protein, total bilirubin, albumin, and serum creatinine. Haematology will include haematocrit, leucocyte count, leucocyte differential count (absolute count), platelet count, and haemoglobin. Urinalysis (dipstick) will assess urine haemoglobin/erythrocytes/blood, protein/albumin, and glucose.

c Serum pregnancy test will be done at baseline and UPT will be done at Day 1, Week 4, 8, 16, 24.

d The vital signs (pulse, blood pressure, respiration rate, and body temperature) will be taken before benralizumab administration, and, if possible, blood drawing and usual asthma controller medication. If it is not logically possible, sufficient time as per clinician discretion should be allotted between phlebotomy and vital signs assessment. For details, please refer to [Section 8.1.3](#).

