## 4 STUDY DESIGN

### 4.1 Overall Design

This is a Phase 4, single-arm, prospective, multicentre, interventional study, designed to assess the safety, tolerability, and effectiveness of benralizumab in adult patients of severe asthma with eosinophilic phenotype in India. The study is planned to meet the postapproval commitment as a regulatory requirement.

Ten centres across India will participate in this study. The investigators will be pulmonologists or chest physicians treating asthma patients. Informed consent will be obtained from all the patients at screening before any study-related procedures are performed. Adult patients of severe asthma with eosinophilic phenotype, who are prescribed benralizumab as an add-on therapy by the treating physician, will be enrolled in the study.

The total study duration will be 24 weeks, including 16 weeks of study treatment, and 8 weeks follow-up ([Figure 1](#)).

- Screening duration: 2 weeks
- Study period: 24 weeks
  - Treatment duration (4 doses): 16 weeks (Day 1, Week 4, Week 8, and Week 16)
  - Post-treatment follow-up duration: 8 weeks (Week 24)

Benralizumab will be provided by AstraZeneca Pharma India Ltd. for the duration of the study.

Participants will be maintained on their currently prescribed therapies including ICS-LABA therapy(ies), throughout the study duration.

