## 5 STUDY POPULATION

Study population will include adult (18 to 75 years of age) male or female patients who have severe asthma with eosinophilic phenotype requiring high dose of ICS and LABA.

Each participant should meet all the inclusion criteria and none of the exclusion criteria to be eligible for the study. Under no circumstances can there be exceptions to this rule. Participants who do not meet the entry requirements are screen failures, refer to [Section 5.4](#).

“Enrolled” means a participant's, or their legally acceptable representative's, agreement to participate in a clinical study after completion of the informed consent process. Prospective approval of protocol deviations to recruitment and enrolment criteria, also known as protocol waivers or exemptions, is not permitted.

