### 5.2 Exclusion Criteria

Patients will be excluded from the study if any of the following criteria apply:

1. Clinically important pulmonary disease other than asthma (eg, active lung infection, chronic obstructive pulmonary disease, bronchiectasis, pulmonary fibrosis, cystic fibrosis etc.) or ever been diagnosed with pulmonary or systemic disease, other than asthma, that are associated with elevated peripheral eosinophil counts (eg, allergic bronchopulmonary aspergillosis/mycosis, Churg-Strauss syndrome, hypereosinophilic syndrome), which can confound the outcome assessment
2. Patients currently enrolled in an interventional clinical study in parallel including those with any biologic treatment
3. Patients who have received any biologic within 30 days prior to the date of informed consent.
4. Known history of allergy or reaction to the benralizumab formulation or excipients (L-histidine, L-histidine hydrochloride monohydrate,  $\alpha$ -trehalose dihydrate, polysorbate 20, water for injection)
5. History of anaphylaxis to any biologic therapy
6. A helminthic parasitic infection diagnosed within 24 weeks before the date informed consent is obtained that has not been treated with, or has failed to respond to, standard of care therapy
7. Acute asthma exacerbation 30 days before the date informed consent
8. Acute asthma exacerbation between screening and first dose of study dose administration.
9. Acute upper or lower respiratory infections requiring antibiotics or antiviral medication within 30 days before the date informed consent
10. Patients with malignancy within 5 years prior to enrolment, with the exception of adequately treated in-situ carcinoma of the cervix, uteri, basal, or squamous cell carcinoma or non-melanomatous skin cancer with active or recent malignancy
11. Any clinically significant abnormal findings in physical examination, vital signs, haematology, clinical chemistry, or urinalysis, which, in the opinion of the investigator, may put the participant at risk because of his/her participation in the study
12. History of current alcohol, drug, or chemical abuse or past abuse that would impair or risk the participant's full participation in the study, in the opinion of the investigator
13. Female patients who are pregnant or lactating or planning a family during the study period.

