No	xx (xx.xx)	(xx.xx, xx.xx)
Missing	xx (xx.xx)	(xx.xx, xx.xx)
Visit x		
Patient Experience any new Exacerbation or change in existing Exacerbation since last visit		
Yes	xx (xx.xx)	(xx.xx, xx.xx)
No	xx (xx.xx)	(xx.xx, xx.xx)
Missing	xx (xx.xx)	(xx.xx, xx.xx)

- The Capital "N" in the column header represents the total number of Evaluable Analysis Set.
- The small "n" in summary statistics represents the total number of patients.
- All Percentages rows are based on the total number of Evaluable Analysis Set.
- 95% CI calculate will be using Clopper-Pearson Exact method.
- Programmer Note: Visit x- Visit 2, Visit 3, Visit 4 and Visit 5
- Source: Listing 16.2.1.1 and Listing 16.2.1.2

Document Title:	Document ID:	BP04-01
Statistical Analysis Plan	Version Number:	3.1
	Effective Date:	25-Nov-2021

Table 14.2.1.3. Summary of Before and After Treatment Exacerbation (Evaluable Analysis Set)

N = xx

**Exacerbation
before study**

N	xx
Missing	xx
Mean (SD)	x.x (x.xx)
Median	x.x
(min, max)	(x,x)
(25th Percentile, 75th Percentile)	(x.xx, x.xx)

**Exacerbation at
end of study**

n	xx
Missing	xx
Mean (SD)	x.x (x.xx)
Median	x.x
(min, max)	(x,x)
(25th Percentile, 75th Percentile)	(x.xx, x.xx)
P-value	x.XXXX

**Annualized
exacerbation
rate**

x.xx

- The column header's capital "N" denotes the total number of Evaluable Analysis Sets.
- The modest "n" in the number of patients suffering from exacerbation.
- The annual rate for each patient was calculated by dividing the total number of exacerbations by the number of days participated in the study and multiplying by 365.
- Source: Listing 16.2.2.1, Listing 16.2.2.2 and Listing 16.2.2.3

Document Title:	Document ID:	BP04-01
Statistical Analysis Plan	Version Number:	3.1
	Effective Date:	25-Nov-2021

Table 14.2.2. Summary of Time to first Exacerbation (Evaluable Analysis Set)

		N=xxx
Patient Asthma Exacerbation, n (%)		
Yes		xx(xx.xx)
No		xx(xx.xx)
Duration of Patient First Asthma Exacerbation (Days)		
n		Xx
missing		xx
Mean (SD)		xx.x (xx.xx)
Median		xx.x
(min , max)		(xx.xx, xx.xx)
(25 th Percentile, 75 th Percentile)		(xx.xx, xx.xx)
Estimate for Time to Response (Days)		
Median		xx.x
95 % CI		(xx.xx, xx.xx)

- The Capital "N" in the column header represents the total number of Evaluable Analysis Set.
- The small "n" in summary statistics represents the total number of patients
- Estimate for Time to Response using Kaplan-Meier method.

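### The only exacerbation follow-up rule starts at consent, so up to 14 untreated, event-free days per patient could enter the denominator of the annualised exacerbation rate

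*Protocol*

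**What the plan says.** Protocol 8.3.1 defines exacerbation follow-up: "Maximum follow-up time for a participant is approximately 24 weeks; defined as the time from enrolment to the date of EOS visit". The same origin applies to a participant lost to follow-up, for whom "this will be defined as the time from enrolment to the time point after which an exacerbation could not be assessed".

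Protocol section 5 defines enrolled as "agreement to participate in a clinical study after completion of the informed consent process". Protocol Table 4 and SAP 2.2.1 and 3.1 agree. On timing, Protocol 4.1 says "Informed consent will be obtained from all the patients at screening before any study-related procedures are performed", and the screening column of Table 1 is headed "Screening (Up to 14 Days Before Day 1". Exclusion 8 (Protocol 5.2) removes patients with "Acute asthma exacerbation between screening and first dose of study dose administration".

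The other exacerbation endpoint in 8.3.1 has a different origin: "Time to first asthma exacerbation will be calculated from baseline (Day 1) to time of first exacerbation". Protocol 9.4.3 and SAP 6.3.2 keep that first-dose origin.

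For the annualised rate, Protocol 9.4.3 gives an exact Poisson interval and refers to a 24-week period, without a start date. SAP 6.3.2 gives no method for the rate. The only formula is the footnote to SAP Table 14.2.1.3, which obtains each patient's rate by "dividing the total number of exacerbations by the number of days participated in the study and multiplying by 365". It does not say when participation starts.

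**The concern.** Time between consent and first dose is immortal time for this analysis. A patient who exacerbates in it is excluded, waivers are not allowed (Protocol section 5), and the rate is computed in the evaluable set, which requires at least one dose. Every analysed patient therefore brings screening days that cannot contain an event and during which no benralizumab has been given. Counting those days as time at risk can only lower the rate.

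This matters because the study has a single arm. No control group shares the same dilution, so the absolute rate is itself the result for this secondary endpoint. The two exacerbation endpoints would also run on different clocks.

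**Working it through.** **The plan's own figure.** End of study is Day 168 ± 7 (Protocol 8.1.3).

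- Day 1 to end of study: 168 / 7 = 24.0 weeks, which matches the stated duration.
- Consent to end of study after a full screening period: (168 + 14) / 7 = 182 / 7 = 26.0 weeks, which does not.

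The 8.3.1 sentence is therefore inconsistent with itself unless consent and Day 1 nearly coincide.

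**Formula.** Let s be days from consent to Day 1 (0 to 14, Table 1) and f be days from Day 1 to the end of follow-up. Events can occur only in f. The consent-based rate divided by the first-dose rate is f / (f + s), so the understatement is s / (f + s).

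**Completers (f = 168).**

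- s = 0: 0%
- s = 7: 7 / 175 = 4.0%
- s = 14: 14 / 182 = 7.7%

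Over the visit window (f = 161 to 175), the 14-day figure runs from 14 / 175 = 8.0% to 14 / 189 = 7.4%. Conversely, correcting the origin raises a completer's rate by at most 14 / 168 = 8.3%. One event in a completer is 365 / 168 = 2.17 per year from first dose and 365 / 182 = 2.01 per year from a consent 14 days earlier.

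**Early leavers with events (s = 14).**

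- Followed to Week 4: 14 / 42 = 33%
- To Week 8: 14 / 70 = 20%
- To Week 16: 14 / 126 = 11%

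**Illustrative cohort.** The note to SAP Table 14.1.1.1 gives 138 patients for analysis and 124 completers, hence 138 − 124 = 14 dosed non-completers. Their follow-up is not given, so I assume a mean of 84 days.

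- Person-days from first dose: 124 × 168 + 14 × 84 = 22,008.
- Added screening days: 138 × 7 = 966, or 138 × 14 = 1,932.
- Fall in a pooled rate: 966 / 22,974 = 4.2%, or 1,932 / 23,940 = 8.1%.

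An assumed true rate of 1.0 per year would read about 0.96 or 0.92.

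**Against sampling error.** 138 patients followed for 168 days give 138 × 168 / 365.25 = 63.5 patient-years. With 63 events, about 1.0 per year, the exact Poisson 95% interval is about 0.76 to 1.27.

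**The case against.** The strongest objection is that the link to the rate is inferred. A reader might conclude that the planned analysis is shown to be biased, but the documents do not go that far. No text says that the 8.3.1 follow-up time is the denominator. That paragraph also fixes where event counting stops, and its next sentence counts patients with events from baseline. The SAP, which in its Introduction takes precedence over the protocol on analysis, uses a different and undefined term.

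A Day 1 reading also has support. Protocol 4.1 and SAP 2.2.1 list the 2-week screening separately from the 24-week study period. Protocol 5.4 treats consenting and entering the study as different steps. Censoring for time to first exacerbation is at 24 weeks.

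This stands as far as it bears on intent, and it makes the bias conditional. It does not remove the defect. The only follow-up definition in either document starts at consent, and the SAP gives a programmer nothing else to use. If Day 1 was meant, the written rule is wrong.

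On size, 14 days is a maximum, and the effect lies well inside sampling error. That is correct, but the confidence interval shows random error only. This error would always favour the drug, and the interval would not reveal it.

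The 33% figure might be taken as the error in the reported result. It is not. It applies to one patient with events, a full 14-day screening and follow-up ending at Week 4. An early leaver without events has a rate of zero on either clock, although in a pooled rate that patient's screening days would still add to the denominator.

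**Conclusion.** The point holds as a conditional bias. Applied as written, the protocol's follow-up rule puts untreated, event-free time into the denominator of the annualised rate. It understates the rate by 0% to 7.7% for a completer on the nominal schedule, and by up to about 8% overall in the illustrative cohort. Individual early leavers with events are affected more. The direction is certain if the rule is used. Whether it would be used is not settled by the documents.

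The size rests on three assumptions. Screening lasts 0 to 14 days, with no distribution given. The 14 dosed non-completers leave at Day 84 on average. For anyone rescreened under Protocol 5.4, consent is dated from the screening that led to dosing.

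Severity is moderate. The endpoint is secondary and descriptive, there is no hypothesis (Protocol 9.1, SAP 6.2), and no threshold or comparator rate depends on it. A reader might infer that the study's conclusions are in doubt, but the documents do not support that. Time to first exacerbation starts at first dose, the proportion with an exacerbation has no person-time denominator, and the primary safety endpoints do not use this clock. It is still more than a missing detail, because the one rule that is stated gives a wrong denominator and conflicts with the Day 1 origin used elsewhere in the same section.

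**What to change.** Add a definition to SAP 6.3.2 and match it in the footnote to Table 14.2.1.3. The denominator of the annualised rate is the number of days from first dose to the end-of-study visit or, if earlier, the last date on which exacerbations could be assessed. Count only exacerbations that start in that window. State that this replaces the enrolment origin in Protocol 8.3.1.

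The SAP is the right place because its Introduction says that its differences from the protocol prevail on analysis. A protocol amendment, with the ethics committee and regulatory approvals in Appendix A 1, is not needed for this purpose.

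The cost is small. Dose dates are already collected (SAP Listing 16.1.6.1), and both exacerbation endpoints would then share one origin. The downside is a slightly less favourable reported rate, by at most 8.3% for a completer at Day 168.

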### **8.3.2 Prebronchodilator FEV1 Through Spirometry**

Pre-BD FEV1 will be recorded by spirometry and performed at screening to confirm the diagnosis of severe asthma.

### **8.3.3 Change in Blood Eosinophils**

Change in blood eosinophil levels from baseline at Week 4, Week 16, and Week 24 will be assessed.

### **8.3.4 Medication Error**

If a medication error occurs in the course of the study, then the investigator or other site personnel informs the appropriate AstraZeneca representatives within **1 day**, ie, immediately but **no later than 24 hours** of when he or she becomes aware of it.

The designated AstraZeneca representative works with the investigator to ensure that all relevant information is completed within **1** (Initial Fatal/Life-Threatening or follow-up Fatal/Life-Threatening) **or 5** (other serious initial and follow-up) **calendar days** if there is an SAE associated with the medication error (see [Section 8.2.4](#)) and **within 30 days** for all other medication errors.

The definition of a medication error can be found in [Appendix B](#).

### **8.3.5 Device Constituent Deficiencies**

- In a combination drug-device study drug (e.g. accessorised prefilled syringe), the device constituent deficiency is an inadequacy of a device constituent with respect to its identity, quality, durability, reliability, safety, or performance. These deficiencies include malfunctions, use errors, and information supplied by the manufacturer.

- For device constituent deficiencies, it is very important that the investigator describes any corrective or remedial actions taken to prevent recurrence of the deficiency.
- A remedial action is any action other than routine maintenance or servicing of a device constituent where such action is necessary to prevent recurrence of a device constituent deficiency. This includes any amendment to the device constituent design to prevent recurrence.
- The investigator is obligated to perform or arrange for the conduct of supplemental measurements and/or evaluations as medically indicated to elucidate the nature and/or causality of the device constituent deficiency as fully as possible. This may include additional laboratory tests or investigations, histopathological examinations, or consultation with other health care professionals.

